9.2 Pharmacodynamics

The relationship between PK and Efficacy and Safety will be explored. The analysis will be described in a separate analysis plan and reported independently.

9.3 Immunogenicity

9.3.1 Anti-nuclear antibodies

Not applicable.

9.3.2 Anti-bimekizumab antibodies

Anti-bimekizumab antibodies (ADAb) will be measured using a three tiered assay approach: screening assay, confirmatory assay and titration assay. Samples confirmed as positive within the confirmatory assay, will be further evaluated in a neutralizing assay to evaluate the potential of the ADAb to neutralize the activity of Bimekizumab (IL17A or IL17F, or both) in-vitro. Samples were taken at baseline, week 4, week 8, week 12, week 16, week 20, week 24, week 36, week 48, week 56 and in subjects who do not enter into the OLE (PS0014) a sample at SFU which is 20 weeks after the last dose.

In subjects randomized to Adalimumab for the first 24 weeks, no ADAb samples will be analysed until week 36, with the exception of the week 24 sample which will be used as a baseline sample.

- Screening, confirmatory and titer cut points of the respective assays will be determined by the bioanalytical laboratory based either on using commercially available drug-naïve samples or on the pre-dose samples of the study itself. In case cut point is being set on commercially available samples, the representative for the study population is being checked. The screening cut point will be used to determine the status of ADA in test sample as above the cut point (ACP) or below the cut point (BCP). Samples presenting ADA levels above the cut point, will be further evaluated in the confirmatory assay, the result of which will be reported as either “confirmed positive” (CP) or “not confirmed positive” (NCP).

- Values \leq screening cut point (BCP) or above the screening cut point and confirmed negative (NCP) are defined as anti-bimekizumab antibody negative
- Values $>$ predefined screening cut point (ACP) and confirmed positive (CP) are defined as anti-bimekizumab antibody positive
- Confirmed positive samples will be titrated, and the titer (reciprocal dilution factor including MRD) reported. The samples (or a subset) will also be subject to a neutralizing assay to evaluate whether the anti-bimekizumab antibody neutralizes the activity of bimekizumab (IL17 A or IL17F or both) in- vitro. This will be reported subsequent to the main DBL and CSR.

Subject Classification:

- For subjects who are negative at baseline, and antibody negative **at all** sampling points post treatment (including SFU) - **pre ADAb negative - treatment emergent ADAb negative**
- For subjects who are negative at baseline, and antibody positive **at any** sampling point post treatment (including SFU) - **pre ADAb negative - treatment emergent ADAb positive**. If a subject has a missing pre-treatment sample (either missing or insufficient volume) at baseline with one or more ADAb positive post-treatment samples will be also classified as **pre ADAb negative - treatment emergent ADAb positive**
- For subjects who are positive at baseline, and antibody negative **at all** sampling points post treatment (including SFU) - **pre ADAb positive - treatment emergent reduced ADAb**
- For subjects who are positive at baseline, and are positive **at any** sampling point post treatment (including SFU) with titer values of the same magnitude as baseline (i.e. \leq than a 2.07 fold difference from the baseline value) - **pre ADAb positive - treatment emergent unaffected ADAb positive**
- For subjects who are positive at baseline, and are positive at any sampling point post treatment (including SFU) with increased titer values compared to baseline (above a 2.07 fold difference increase from baseline value which will be defined within the validation of the assay and will be included in the TFLs and/or SAP when available) - **pre ADAb positive - treatment emergent ADAb boosted positive**.
- For Subjects who have a positive pre-treatment sample and some post-treatment samples are missing, while other post-treatment samples are ADAb negative, **the subject will be classed as inconclusive**.

For the interim analysis at Week 56, SFU data will not be included.

Analysis

Immunogenicity will be assessed through summary tables and figures, and listing of individual results by subject. All analyses will be run on the safety population, unless specified otherwise.

- Number and percentage of subjects with anti-bimekizumab antibody level above the specified cut point at the time of each visit, separated by treatment group
- Number and percentage of subjects with anti-bimekizumab antibody level above the specified cut point at any visit during the treatment period, separated by treatment group.

- The time-point of the first occurrence of anti-bimekizumab anti-body positivity during the treatment period) will be summarized for each treatment group. A plot of the Titre versus elapsed time will be plotted
- All individual subject-level anti-bimekizumab antibody results will be listed.
- The number and percentage of subject in each of the 6 categories will be tabulated and separated by treatment group, with an additional category combining subjects who are **pre ADAb negative - treatment emergent ADAb positive** and **- pre ADAb positive - treatment emergent ADAb boosted positive, summarized as Total treatment emergent**. In addition, the number and percentage of subjects who are pre ADAb positive will be summarized (combination of **pre ADAb positive - treatment emergent reduced ADAb, pre ADAb positive - treatment emergent unaffected ADAb positive and pre ADAb positive - treatment emergent ADAb boosted positive**).
- The prevalence of immunogenicity, separated by treatment group, and defined sub-category, will be reported per time point, defined as (cumulative) proportion of subjects having confirmed positive ADAb samples at any point up to and including that time point. Missing samples will not be included in the denominator.
- The time to achieving treatment-emergent ADAb positivity, separated by treatment group and defined sub-category, will be analyzed based on Kaplan-Meier approach, subjects will be considered to have an event at time where treatment emergent ADAb positive is first achieved. Subjects classified as treatment-emergent ADAb negative will be censored at time of last available ADAb result.
- A summary of PASI 90 responder, separated by treatment group and defined sub-category, at weeks 16 and 24 as a function of ADAb titer will be presented graphically. This will be repeated for PASI 100 and 75 responders.
- Individual plots of Bimekizumab Concentrations/ADAb titer and % Change from baseline (all Y-axes) versus time (x-axis) for the full treatment period, including SFU where a patient has not progressed into the OLE. Plots should be labeled and grouped into the 6 sub-categories.
- Spaghetti plots of ADAb titer (Y-axis) against time (X-axis), separated by treatment group for all ADAb positive subjects, including baseline positive subjects.
- Box plots of all Bimekizumab concentrations where ADA titers exists versus ADA titer classification (group 1 > ; group 2 > ; group 3 >) presented on a linear scale. Cut-points will be determined on availability of titre data

For purposes of efficacy subgroup analyses based on anti-bimekizumab antibody status, two categories will be used:

- Anti-bimekizumab antibody positive – This is defined as subjects who have anti-bimekizumab antibody levels above the specified cut point on at least 2 time points while on treatment (ie, excluding Baseline, excluding SFU).
- Anti-bimekizumab antibody negative – Subjects who are not defined as anti-bimekizumab positive (as described above) will be defined as anti-bimekizumab antibody negative.

The rationale for requiring at least 2 time points in which anti-bimekizumab antibody levels are above the specified cut point is to exclude those subjects who have only one occurrence of anti-bimekizumab antibody levels during the course of treatment. Including such subjects would increase the number of anti-bimekizumab antibody positive subjects with potentially no impact on efficacy.

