4.2.1.4 Handling missing data for subgroup analyses

For subgroup analyses specified in Section 4.8, NRI will be used for responder variables. Only descriptive statistics will be provided.

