4.2.1.5 Missing Data Overview and Summary

In summary, the approaches listed below will be used in this study for handling missing data for efficacy variables as appropriate:

- Non-responder imputation (NRI): Subjects who have missing data at the time point of interest are treated as though they did not respond to the treatment.
- Multiple Imputation (MI) – Markov Chain Monte Carlo (MCMC) / Monotone Regression: Using multiple imputation methodology, intermittent missing data are imputed based on the MCMC method, and monotone missing data are imputed using monotone regression. Note: for all analyses and summaries using MI, subjects with no baseline value will be excluded.
- Last observation carried forward (LOCF): Post-Baseline missing data are imputed by carrying forward the last available observation (including Baseline).

- Observed case (OC): Missing data are not imputed. Only subjects with available data who have not discontinued study treatment at the given time point are considered.

The following table depicts which missing data handling approaches should be used based on variable priority (primary, secondary, other) and variable type (responder, continuous, ordinal).

Table 4–1: Missing data handling approach by variable priority and type

Variable Priority	Variable Type	NRI	MI (MCMC/ Monotone Regression)	MI (MCMC/ Reference-based)	LOCF	OC
Primary	Responder	P	S ^a	n/a	S	S
Secondary	Responder	P	S ^a			S
	Continuous		P		B	S
Other	Responder	P				S ^{b, c}
	Continuous ^e		P		B	
	Ordinal					P ^d

P=Primary method, S=Sensitivity method, B=Backup method, NRI=Non-responder imputation, MI=Multiple imputation, MCMC=Markov Chain Monte Carlo, LOCF=Last observation carried forward, OC=Observed Case
Note: Backup method is only applicable when the primary method is unable to converge due to challenges with the imputation model.

^a Imputation method is applied on continuous data, and responder variable is derived from the continuous variable based on complete data set.

^b Only applies to by-visit summaries of variables that are in the multiplicity-controlled testing procedure.

^c Includes IGA response, PASI75, PASI90 and PASI100.

^d Includes Patient Global Assessment of PSO, IGA score and EQ-5D-3L responses.

^e For PASE, OC is the primary analysis method.

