4.8 Examination of subgroups

Subgroup analyses will be performed on PASI75/90/100 response rates and IGA, using by visit summaries only. The following subgroups for analysis will be determined using baseline data:

- Age (<40 years, 40 to <65 years, ≥65 years)

- Gender (male, female)
- Disease duration (<median, ≥median)
- Region (North America [Canada, USA], Western Europe [Germany], Central/Eastern Europe [Czech Republic, Hungary, Poland, Russian Federation], Asia/Australia [Australia, Republic of Korea, Taiwan])
- Weight (≤100 kg, >100 kg)
- BMI (<25 kg/m², 25 to <30 kg/m², ≥30 kg/m²)
- Prior systemic phototherapy or chemotherapy (yes, no)
- Prior biologic exposure (yes, no)
- Prior systemic therapy of any kind (yes, no)
- Baseline disease severity (PASI<20, PASI≥20)
- Antibody positivity (negative, positive)

Antibody positivity is the only subgroup that is not determined by Baseline data. It will be presented in a separate table.

The definition of prior systemic therapy of any kind is that if a subject received previous biologic therapy, previous systemic therapy (non-biologic), or previous systemic chemotherapy or phototherapy. Subjects who never received previous biologic therapy, previous systemic therapy (non-biologic), or previous systemic photochemotherapy or phototherapy will be classified as not receiving prior systemic treatment for psoriasis.

In addition, in order to assess whether an early response to treatment is predictive of response at later time points, subgroup analyses will be performed for the RS on PASI90/100 and IGA over time using the following early response subgroups:

- PASI75 responders (OC) at Week 4 (yes, no) to predict PASI90/100 and IGA (NRI) through initial and maintenance treatment period
- PASI90 responders (OC) at Week 16 (yes, no) to predict PASI100 (NRI) through maintenance treatment period

All summaries will be based on imputed data as appropriate and will include descriptive statistics only.

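### The antibody-negative efficacy subgroup is a catch-all, so with NRI it absorbs early bimekizumab dropouts and makes antibody-positive subjects look better than they are

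*SAP*

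**What the plan says.** - **Positive.** SAP 9.3.2 requires antibody levels "above the specified cut point on at least 2 time points while on treatment (ie, excluding Baseline, excluding SFU").
- **Negative.** Everyone else: "Subjects who are not defined as anti-bimekizumab positive (as described above) will be defined as anti-bimekizumab antibody negative". This definition has no missing or inconclusive class and no minimum number of results.
- **Timing of status.** SAP 4.8 acknowledges that "Antibody positivity is the only subgroup that is not determined by Baseline data". The subgroup results are by-visit summaries.
- **Missing responses.** SAP 4.2.1.4: "NRI will be used for responder variables. Only descriptive statistics will be provided". SAP 4.2.1.5 defines the rule: "Subjects who have missing data at the time point of interest are treated as though they did not respond to the treatment".
- **Adalimumab arm.** SAP 9.3.2: "no ADAb samples will be analysed until week 36, with the exception of the week 24 sample", and that Week 24 sample serves as a baseline. SAP 3.6 reports by treatment group and shows adalimumab only to Week 24.
- **Withdrawals.** Protocol 8.4 gives withdrawing subjects the Week 56 assessments, which include an antibody sample. SAP 3.3 assigns that sample to the next scheduled antibody visit.

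**The concern.** Being positive requires staying in the study long enough to give two positive samples. A bimekizumab subject who leaves before that is negative by default, and NRI then makes the same subject a non-responder. Dropout alone lowers the negative rate, whatever antibodies do. This is guaranteed-time bias.

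Status also looks ahead. Samples at Weeks 36, 48 and 56 can decide who counts as positive in the Week 16 row, and only subjects who remain can supply them.

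At stake is the reading of the table that should show whether antibodies reduce efficacy. The bias runs toward reassurance. If antibodies themselves led to early stopping, those subjects would still be labelled negative unless two positive samples had been recorded first.

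The same SAP section is more careful elsewhere. Its immunogenicity classes include an inconclusive group for some subjects with missing samples, and its prevalence calculation leaves missing samples out of the denominator. The stated rationale supports requiring two positive samples; it does not justify calling subjects with too few results negative.

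**Working it through.** The plan gives no figure for antibody positivity, for dropout or for this subgroup, so there is none to reproduce. The 75% PASI90 and 85% IGA rates for bimekizumab are in SAP 2.4.

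**1. When a subject can become positive.** SAP 9.3.2 samples at Weeks 4, 8, 12, 16, 20, 24, 36, 48 and 56: nine on-treatment time points. The earliest second scheduled sample is Week 8. A withdrawal-visit sample can supply the second time point sooner.

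**2. The mechanism by hand.** Take 300 bimekizumab subjects with an overall NRI PASI90 rate of 75% and no antibody effect. Let d be the share who leave with no chance of two positive samples, and q the share positive among the rest (both assumed).

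- Positive rate = 0.75/(1−d)
- Negative rate as planned = [0.75/(1−d)] × (1−q)(1−d) / [(1−q)(1−d) + d]

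With q = 30% and d = 5%, the positive rate is 0.75/0.95 = 78.9%. The negative group holds 300 × 0.95 × 0.70 = 199.5 classifiable subjects plus 15 dropouts, so its rate is 78.9% × 199.5/214.5 = 73.4%. The gap is +5.5 points, and the true value is 0. With q = 30%, d = 1% gives +1.1 and d = 2% gives +2.2.

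Now let antibodies truly cost 5 points (q = 30%). The classifiable negative rate is pn = 0.75/(1−d) + 0.05q, the positive rate is pn − 0.05, and the planned negative rate is pn(1−q)/[(1−q) + d/(1−d)]. For d = 2%, pn = 78.0%, the positive rate is 73.0% and the planned negative rate is 75.8%. The table shows −2.8 instead of −5. It shows −3.9 at d = 1% and +0.6 at d = 5%.

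Here d is not total dropout. If 10% drop out uniformly over 56 weeks, the share gone before Week 8 is 10% × 8/56 = 1.4%. Later leavers add to the bias because they too had less time to give two positive samples.

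**3. Simulation with full follow-up.** Assumptions: no antibody effect; 40% ever positive, onset Weeks 4 to 24, persistent afterwards; 85% response; dropout uniform over 56 weeks and independent of antibodies; response set to 0 after dropout. Entries are the positive-minus-negative gap in points at Weeks 16 / 24 / 56.

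| Dropout | Planned rule, withdrawal sample not counted | Planned rule, withdrawal sample counted | Results up to the visit, at least 2 evaluable, NRI kept (withdrawal sample not counted) |
|---|---|---|---|
| 6% | 2.3 / 2.9 / 3.1 | 1.9 / 2.4 / 2.3 | 0.6 / 1.4 / 2.0 |
| 10% | 3.8 / 4.7 / 5.0 | 3.3 / 4.0 / 3.6 | 1.1 / 2.2 / 3.3 |
| 15% | 5.4 / 7.0 / 7.1 | 5.0 / 5.8 / 5.4 | 1.6 / 3.3 / 4.6 |

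Repeat runs differ by up to about 0.2 point; the 3.3 at 10% dropout came out at 3.4 on repeat. With the last rule applied only to subjects still on treatment at the visit, the gap is about 0.

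**4. Adalimumab.** The samples that can count are Weeks 36, 48 and 56, all after the switch. The arm is displayed to Week 24. Any positive label on those visits therefore comes from antibodies measured after the displayed period.

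**The case against.** **The withdrawal sample.** It is tempting to say that everyone who stops before Week 8 is automatically negative. That goes too far: a positive Week 4 sample and a positive withdrawal-visit sample are two time points under SAP 3.3 and 9.3.2. Counting the withdrawal sample trims the bias (5.0 to 3.6 at Week 56 with 10% dropout) but does not remove it.

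**Size.** SAP 4.2.1 expects few discontinuations before Week 16. With 300 subjects split 120/180 at 85% response, the standard error of the difference is √[0.85 × 0.15 × (1/120 + 1/180)] = 4.2 points, larger than the bias at 6% dropout. This stands as a limit on importance. The bias is nevertheless systematic, always runs the same way in this model, and adds to the noise.

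**Other displays.** SAP 9.3.2 also plans graphs of PASI response against titer at Weeks 16 and 24, and individual plots. These help, but they do not correct the subgroup table.

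**Adalimumab.** A reader might infer that adalimumab subjects labelled negative pull down the negative rate and so flatter bimekizumab positives. The documents do not support this: results are by treatment group, so that arm contributes 0 to a bimekizumab rate. Nor is the arm simply untested, since three post-switch samples are analysed. What remains is that its split by antibody status up to Week 24 is uninformative. SAP 4.8 does not say whether the antibody table will have adalimumab columns; that they may appear is inferred from SAP 3.6.

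**Conclusion.** The concern holds for the bimekizumab groups. The catch-all negative class, look-ahead status and NRI together favour antibody-positive subjects. With no true effect the spurious advantage is about 2 to 3 points at 6% dropout, 3.4 to 5 at 10% and 5 to 7 at 15%, the lower values applying when withdrawal-visit samples are counted. These sizes rest on assumed positivity, onset and dropout; at the low early dropout the SAP expects, the Week 16 effect is probably small.

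It would be wrong to infer that the trial's conclusions are at risk. The table is descriptive, and no co-primary or hierarchical test uses antibody status. It would also be wrong to infer that a minimum-sample rule is a complete cure: with NRI kept, the gap at 10% dropout is still 1.1 points at Week 16 and 3.3 at Week 56. The change is worth making because it is cheap and the present bias can hide a modest loss of efficacy.

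**What to change.** In SAP 9.3.2 and 4.8:

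1. Limit the antibody-status efficacy table to subjects randomised to bimekizumab.
2. At each visit, classify by on-treatment results up to that visit, including mapped withdrawal samples. Require at least two evaluable results, keep the two-positive rule, and show all others as not evaluable.
3. Compare positive with negative among subjects still on treatment with data at that visit, using the observed-case definition already in SAP 4.2.1.5 or a fixed landmark. Keep the NRI rows alongside.

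The cost is SAP wording and a derivation change, with no new data. The drawbacks are a small non-evaluable group, no classification before Week 8, and a comparison conditional on remaining on treatment. That comparison would miss an antibody effect acting through discontinuation, which is why the NRI rows should stay beside it.

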10 SAFETY ANALYSES

All safety summaries and listings will be created using all subjects in the SS.

The SS, BKZ Set, BKZ Week 24 Set and MS will be used for summaries of safety data.

It was noted during the conduct of the study that approximately 24 subjects received incorrect Placebo/Active treatment at Visit 20. All subsequent treatments were administered per protocol. The impact of this on safety is expected to be minor and no adjustments will be made to the summaries of safety data. The actual treatments received will be shown in the data listings.

10.1 Extent of exposure

Summaries for exposure will be provided. This consists of a descriptive summary of study medication duration in days. In addition, total study medication duration and time at risk will be summarized in years by treatment group and treatment period (i.e., through initial treatment period, Week 24, and initial and maintenance treatment period). The summary of exposure through the initial and maintenance treatment period will be on BKZ set. The cumulative study medication duration will be summarized for subjects exposed for given durations of time, with four weekly categories through initial treatment period and Week 24. For the cumulative duration through initial and maintenance treatment period the following categories for duration will be used:

- >0 weeks
- ≥ 16 weeks
- ≥ 24 weeks
- ≥ 40 weeks
- ≥ 56 weeks

Definitions for study medication duration and time at risk in days are provided below for each period. Time at risk will be summarized in years. Time at risk in years is calculated by dividing the time at risk in days by 365.25.

Throughout this section, date of last clinical contact for each subject is defined as the maximum of (last visit date including SFU visit, last imputed AE start date, date of study termination or completion, last date of study drug administration).

10.1.1 Exposure during the initial treatment period for SS

Definitions for study medication duration (days) and time at risk (days) during the initial treatment period are provided as follows:

Study medication duration (days)

- Date of last dose of active medication in the Initial treatment Period – date of first dose in the Initial Treatment Period + 28 days for bimekizumab Q4W/ +14 days for adalimumab

Note: If date of last dose of active medication in the Initial Treatment Period + 28 days/ 14 days extends to a date beyond the date of the first dose in the Maintenance Treatment Period, then this calculation reverts to:

- Date of first dose in the Maintenance Treatment Period – date of first dose in the Initial Treatment Period + 1.

Note: For subjects who die during the Initial Treatment Period, if date of last dose of active medication in the Initial Treatment Period + 28 days/ 14 days extends to a date beyond the date of death, then this calculation reverts to:

- Date of death – date of first dose in the Initial Treatment Period + 1.

For subjects who permanently discontinue study treatment:

- Date of last dose of active medication – date of first dose + 28 days for bimekizumab Q4W/ +14 days for adalimumab.

Note: If date of last dose of active medication + 28 days/ 14 days extends to a date beyond the final visit date (including PEOT, but not including SFU), then this calculation reverts to:

- Final visit date (including PEOT, but not including SFU) – date of first dose + 1.

Time at risk (days)

- For subjects who complete the final visit of Initial Treatment Period and continue into the Maintenance Treatment Period: Date of first dose in the Maintenance Treatment Period – date of first dose in the Initial Treatment Period + 1.
- For subjects who discontinue on or prior to the final visit of the Initial Treatment Period, use the minimum of the following:
 - Date of last dose of Initial Treatment Period – date of first dose in the Initial Treatment Period + 140 days.
 - The total number of days in the Initial Treatment Period.
 - Date of last clinical contact – date of first dose in the Initial Treatment Period + 1.
- For subjects who die prior to the final visit of the Initial Treatment Period: Date of death – date of first dose in Initial Treatment Period +1.

